- P. Any Screening Stage 2 lab testing can be obtained from Day -35* to Day -1 during Screening. Overnight fasting lipid panel may be obtained on Day -35 if subjects are fasting as per institutions standard of care procedure, which must be clearly documented in the source documents. ***NOTE: Subjects must not be requested to come in fasting for study specific assessments prior to signing the informed consent. Results of these labs will not need to be reviewed before Screening Stage 2 or Day 1.**
- Q. Subjects with positive hepatitis B core antibody will undergo testing for hepatitis B DNA and hepatitis B surface antibody during Screening. Subjects with known hepatitis C will also undergo testing for hepatitis C RNA viral load (Refer to Section 6.4.14 for details on Serology testing). During re-screening, if there is already a negative result from prior screening, the hepatitis B, C, or E or HIV serologies do not need to be repeated.

SCHEDULE OF STUDY PROCEDURES (CONTINUED)

- r. Ileocolonoscopy and biopsies will be performed after subject's eligibility is confirmed (upon review of CDAI score prior to the start of bowel preparation and no exclusionary criteria are met). Ileocolonoscopy does not need to be repeated for a rescreening if the ileocolonoscopy is within 28 days of Day 1 of the re-screen and if the SES-CD score is qualifying.
- s. Stool infectious studies to include: C. difficile, other bacteria (including Shigella, Salmonella, Yersinia, Enterohemorrhagic or Enteropathogenic or Enterohemorrhagic E. coli O157, and Campylobacter), and ova and parasite.
- t. [REDACTED]
- u. [REDACTED]
- v. [REDACTED]
- v. Obtained prior to ileocolonoscopy (to assess eligibility criteria at Screening). Any time after Screening Stage 1 and once a minimum of 5 entries have been confirmed, the clinician assessments can be completed. Should be performed prior to the start of bowel preparation for the Screening Stage 2 endoscopy. The Screening Stage 1 weight and hematocrit result will be used to calculate this CDAI score.
- w. Subject must have completed their electronic diary (or paper diary if electronic diary is not available) at least 5 out of 7 days prior to Screening Stage 2.

Note: See [Appendix 13](#) for general guidance on study conduct during the COVID-19 pandemic. Variations from planned assessments will still constitute protocol deviations.

TABLE OF CONTENTS

PROTOCOL SYNOPSIS	2
LIST OF ABBREVIATIONS AND DEFINITION OF TERMS	29
1. INTRODUCTION	32

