405. Subject is taking non-CD concomitant prescription medications that have started or have had a dose adjustment within 4 weeks prior to Day 1 (with the exception of corticosteroids as discussed in inclusion criterion #107, antibiotics for recent infections, sedating agents for ileocolonoscopy, hormonal contraceptives, hormone replacement therapy, vitamin D, insulin therapy, and replacement thyroid hormone - see Section 6.4.29)
406. Subject is taking non-CD over-the-counter medications or dietary supplements that have started or have had a dose adjustment within 2 weeks prior to Day 1 (with the exception of up to 3 times per week use of non-steroid anti-inflammatory drugs or acetaminophen used on an as needed basis, aspirin up to 325 mg per day for cardiovascular prophylaxis, and over-the-counter doses of vitamin D - see Section 6.4.29)

Exclusion Criteria Pertinent to Infections:

500. Subject is positive for:
- hepatitis B virus (HBV) surface antigen
 - hepatitis B virus core antibody (unless subject has positive hepatitis B surface antibody and undetectable serum hepatitis B DNA)
 - hepatitis C virus (HCV) antibody unless: a) there is evidence of undetectable viral load measured twice six months apart after completion of treatment regimen and b) viral load during Screening is undetectable
 - hepatitis E Immunoglobulin M (IgM) antibody
 - human immunodeficiency virus (HIV) antibody
501. Subject has had a live viral vaccine (e.g., MMR, varicella zoster, herpes zoster, oral polio virus, FluMist, attenuated typhoid fever vaccine, attenuated rotavirus vaccine, or any investigational live vaccine) within 4 weeks prior to Screening and/or is unwilling or unable to avoid live viral vaccines during the study and for 8 weeks following completion of the study; subject must be willing to avoid contact with any household member who has been vaccinated with a live attenuated vaccine within 2 weeks after vaccination
502. The subject has or may have untreated active or latent TB as evidenced by any of the following:
- Two indeterminate or two positive QuantiFERON®-TB Gold result within 90 days prior to screening or during the Screening Period, without having completed an adequate treatment for latent or active TB before Screening **OR**
 - Chest X-ray or equivalent chest imaging within 90 days prior to Screening in which active or latent pulmonary TB cannot be excluded.
- Refer to Section 6.4.15 for rationale and required documentation for repeat testing.

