406. Subject is taking non-CD over-the-counter medications or dietary supplements that have started or have had a dose adjustment within 2 weeks prior to Day 1 (with the exception of up to 3 times per week use of non-steroid anti-inflammatory drugs or acetaminophen used on an as needed basis, aspirin up to 325 mg per day for cardiovascular prophylaxis, and over-the-counter doses of vitamin D - see Section 6.4.29)

Exclusion Criteria Pertinent to Infections:

500. Subject is positive for:
 - a. hepatitis B virus (HBV) surface antigen
 - b. hepatitis B virus core antibody (unless subject has positive hepatitis B surface antibody and undetectable serum hepatitis B DNA)
 - c. hepatitis C virus (HCV) antibody unless: a) there is evidence of undetectable viral load measured twice six months apart after completion of treatment regimen and b) viral load during Screening is undetectable
 - d. hepatitis E Immunoglobulin M (IgM) antibody
 - e. human immunodeficiency virus (HIV) antibody
501. Subject has had a live viral vaccine (e.g., MMR, varicella zoster, herpes zoster, oral polio virus, FluMist, attenuated typhoid fever vaccine, attenuated rotavirus vaccine, or

any investigational live vaccine) within 4 weeks prior to Screening and/or is unwilling or unable to avoid live viral vaccines during the study and for 8 weeks following completion of the study; subject must be willing to avoid contact with any household member who has been vaccinated with a live attenuated vaccine within 2 weeks after vaccination

502. The subject has or may have untreated active or latent TB as evidenced by any of the following:
- a. Two indeterminate or one positive QuantiFERON®-TB Gold result within 90 days prior to screening or during the Screening Period, without having completed an adequate treatment for latent or active TB before Screening **OR**
 - b. Chest X-ray or equivalent chest imaging within 90 days prior to Screening in which active or latent pulmonary TB cannot be excluded.
Refer to Section 6.4.15 for rationale and required documentation for repeat testing.
- A subject who has a history of latent or active tuberculosis (TB) may be eligible for the study if criteria outlined in Section 6.4.15 are met.
503. Subject has:
- a. an active, clinically significant bacterial, parasitic, fungal, mycobacterial (including atypical infection), or viral infection, except for local skin or nail bed infection, within 30 days prior to Day 1

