6.3. Procedures by Visit

6.3.1. Screening

6.3.1.1. Screening Stage 1

Screening Stage 1 visit assessments will be performed between 35 and 1 days prior to Day 1. Initial eligibility assessments will be reviewed and confirmed by the investigator prior to each subject continuing on to the endoscopy with biopsy assessments at Screening Stage 2.

The following procedures will be performed at Screening Stage 1:

- Written informed consent (signed and dated) after the nature of the study has been explained and before any study procedure is performed
- Review of inclusion and exclusion criteria
- Medication and medical history
- Vital signs
 - Heart rate (HR) and systolic and diastolic blood pressure (BP)
 - Respiratory rate

- Body Temperature
- 12-lead ECG
- Physical examination (including fistula exam to determine drainage status if the subject has a fistula) to be conducted according to local practice
- Height and weight
- Chest X-ray (unless one has been performed within 3 months of Screening, documented to be negative, and reviewed by investigator. Subjects who have had a chest X-ray within 3 months prior to Screening will not require a repeat X-ray unless subject is deemed to be at high risk of recent pulmonary infection)
- Blood collection
 - Hematology
 - Serum chemistry
 - FSH (postmenopausal females)
 - Viral hepatitis and human immunodeficiency virus [HIV] serology panel (Refer to Section 6.4.14 for additional details)
 - QuantiFERON®-TB Gold [unless an exam has been done with negative findings within 90 days prior to Screening or subject has a history of latent TB that has been adequately treated within the prior 5 years (Refer to Section 6.4.15 for additional details)] - If the QuantiFERON®-TB Gold result is indeterminate, a repeat QuantiFERON®-TB Gold will be performed.
 - Labs required for Screening Stage 2 can be collected during this visit if the subject happens to be fasting during this visit. Subjects should not be instructed to come in fasting.
- Urine collection
 - Urinalysis
 - Pregnancy test for females of childbearing potential – If urine b-hCG test is positive, confirmation with serum b-hCG test is required
- Fecal collection
 - Fecal infectious studies [C. difficile, other bacteria (including Shigella, Salmonella, Yersinia, E. coli O157, and Campylobacter), and ova and parasite]
- Review concomitant medications
- Adverse event assessment (AEs, SAEs, Adverse Events of Special Interest)

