6.4.15. Tuberculosis (TB) Test

A subject with a history of latent TB or signs of latent TB on chest X-ray or with positive result on QuantiFERON®-TB Gold test may be eligible for the Study if the subject:

1. has completed an adequate course of treatment (e.g., 9-month course of INH or equivalent therapy for latent TB) within 5 years (3 years in countries where TB is endemic) years prior to Screening, the documentation for which must be included in the source document and reviewed by the PI, or currently undergoing an appropriate course of treatment (e.g., 9-month course of INH or equivalent therapy for latent TB) and has completed at least 3 months of this treatment before Screening with adequate compliance (as determined by the investigator), and
2. has not lived in a region with high prevalence of multidrug-resistant TB.
3. A subject with a history of latent TB should not undergo TB testing during screening but must undergo X-ray if none has been performed within 90 days prior to screening.

A subject with history of active TB may be eligible for the Study if:

- He or she has completed an adequate course of treatment within 5 years (3 years in countries where TB is endemic) prior to Screening (the documentation for which must be included in the source document and reviewed by the PI),
- The QuantiFERON®-TB Gold within 90 days of screening is negative, and
- The subject has not lived in a region with high prevalence of multidrug-resistant TB

A QuantiFERON®-TB Gold test will be conducted at Screening to assess for signs of latent TB unless:

- a. an exam has been done with negative findings within 90 days prior to screening, or
- b. Subject has a history of latent TB that has been adequately treated (e.g., with ≥ 9 months of INH or equivalent therapy or currently being treated with an appropriate course of treatment.
- c. In either case a or b, there must be documentation in the source document, which must be reviewed by the investigator.

If the QuantiFERON®-TB Gold result is indeterminate, then repeat QuantiFERON®-TB Gold. If results from both tests are indeterminate the subject should be excluded.

In case of a suspected false-positive QuantiFERON®-TB Gold result (e.g., a negative result by the local laboratory and suspicion of sample processing error, both of which must be documented in the source document), a second sample may be sent to the central laboratory and the result of the second test will be used.

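### The TB-test exclusion and the skin-cancer stopping rule are each stated in two inconsistent ways in the current protocol, and in each case the looser statement is the wrong one

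*Protocol*

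**What the plan says.** **TB test.** In the synopsis, exclusion 502 opens with "The subject has or may have untreated active or latent TB as evidenced by any of the following". Its first limb names "Two indeterminate or two positive" QuantiFERON results without completed adequate treatment. In Section 4.2 the corresponding limb, 502a, begins "Two indeterminate or one positive". The chest-imaging limb is the same in both places, and both carry the pointer "Refer to Section 6.4.15 for rationale and required documentation for repeat testing".

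Section 6.4.15 sets out what a positive result means. A subject "with positive result on QuantiFERON®-TB Gold test may be eligible for the Study if the subject" has completed adequate treatment, or has had at least 3 months of ongoing treatment, and has not lived where multidrug-resistant TB is highly prevalent. For a suspected false positive, the example given is "a negative result by the local laboratory and suspicion of sample processing error, both of which must be documented in the source document"; then "a second sample may be sent to the central laboratory and the result of the second test will be used". Section 6.3.1.1 (Screening Stage 1) orders a routine retest in one case only: "If the QuantiFERON®-TB Gold result is indeterminate, a repeat QuantiFERON®-TB Gold will be performed".

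**Skin cancer.** Section 6.5.1 says that non-laboratory adverse events of special interest, as defined in Section 7.1.4, should lead to stopping study drug, and it excepts non-melanoma skin cancer without condition. Section 7.1.4 excepts it only once fully resected.

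**Washout (side note).** For vedolizumab, ustekinumab, mycophenolic acid, tacrolimus, sirolimus and cyclosporine, synopsis exclusion 400 requires the longer of 60 days or 5 half-lives. Section 4.2 requires 60 days.

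**The concern.** The first rule governs who enters and the second governs who stops study drug. Section 1.4 lists tuberculosis and non-melanoma skin cancer among the events seen with a systemic JAK inhibitor, although it expects lower risk with TD-1473 because systemic exposure is low.

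A site working from the synopsis bullet could pass an untreated subject with a single positive test. A site working from Section 6.5.1 could keep a subject with an unresected skin cancer on drug. The sponsor might not learn of the second case quickly: Sections 7.1.4 and 7.4.3 exempt non-melanoma skin cancer from 24-hour special-interest reporting, so unless the event is also serious, that route raises no prompt alert.

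The wording also bears on reporting. SAP Sections 3.2.1 and 3.2.3 plan listings of eligibility exceptions and protocol deviations, and whether such a subject appears there depends on which text governs.

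**Working it through.** The plan states no figure to reproduce for the two main rules, so the check sets the texts side by side. All are in current text of the protocol dated 09 June 2020. The supplied documents contain no precedence rule or amendment entry that settles the differences, and the SAP does not address them.

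**TB rule, QuantiFERON limb, subject without adequate or ongoing TB treatment**

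| Results | Synopsis 502 | Section 4.2, 502a | Section 6.4.15 |
|---|---|---|---|
| One positive, no repeat | not excluded | excluded | no route to eligibility |
| One positive, documented suspected false positive, negative repeat | not excluded | excluded if read literally | second result is used, so not excluded |
| Two positive | excluded | excluded | no route to eligibility |
| Two indeterminate | excluded | excluded | excluded |

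Row 1 is the conflict. Section 6.4.15 sides with Section 4.2, since it admits a positive only with treatment or through the documented false-positive route. Section 6.3.1.1 points the same way: a repeat is routine only after an indeterminate result, so no standard procedure would generate the second positive that the synopsis asks for. The stem of 502 does not rescue the synopsis, because it is tied to the list beneath it, and that list carries the two-positive threshold.

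Row 2 is a smaller mismatch in the other direction. Read alone, 502a excludes a subject whom Section 6.4.15 would allow. Changing only the synopsis would leave this in place.

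**Skin-cancer rule**

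| Non-melanoma skin cancer | Section 6.5.1 | Section 7.1.4 |
|---|---|---|
| Fully resected | exempt from stopping | exempt from stopping |
| Not fully resected | exempt from stopping | should stop study drug |

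The difference is confined to the second row. Section 7.1.4 is the text that Section 6.5.1 itself cites. Exclusion 607 also requires complete resection before it tolerates a history of skin cancer, which fits the Section 7.1.4 version.

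**Washout**

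Let *h* be the half-life in days. The two rules differ only when 5*h* > 60, that is, when *h* > 60 / 5 = 12 days; the synopsis then adds 5*h* − 60 days. The waiver for a documented undetectable drug level covers 2 of the 6 agents (vedolizumab and ustekinumab), leaving 6 − 2 = 4 without it. The documents give no half-lives, so the calculation stops here.

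**The case against.** The strongest reply is that neither pair forces a site into an impossible position. Each is a stricter and a looser statement, and following the stricter one satisfies both. Section 6.4.1 allows enrolment only if no exclusion criterion is met, so an untreated single-positive subject is excluded by 502a whatever the synopsis omits. The synopsis and Section 3.1 both direct the reader to Sections 4.1 and 4.2 for the criteria, and synopsis 502 itself points to Section 6.4.15. Section 6.5.1 does not tell anyone to continue drug with an unresected lesion; it merely leaves that event out of its own stopping sentence, and it lets the investigator discontinue a subject at any time.

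Most of this stands, and it sets the size of the point. A reader might infer that the protocol authorises enrolling untreated single-positive subjects, or requires treatment to continue through unresected skin cancer. The documents do not support either reading. What the reply does not do is make the two looser statements correct: the synopsis still prints the wrong threshold, and Section 6.5.1 still prints an exemption wider than its own source.

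A reader might also infer from exclusion 400 that Section 4.2 shortens the washout for the biologics. That needs half-lives, which the documents do not give, and the pointer in criterion 400 is redacted.

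**Conclusion.** The point holds as a drafting inconsistency in two subject-protection rules. The synopsis TB threshold (two positives instead of one) and the Section 6.5.1 exemption (all non-melanoma skin cancer instead of fully resected only) are wrong as written. The exposure is limited to sites that rely on those two texts alone, and the number of subjects affected cannot be derived from the documents.

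Nothing here alters sample size, power, type I error or the between-arm comparison, and the documents do not show that any subject was wrongly enrolled or kept on drug.

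The SAP Introduction records a decision to terminate the study early. If enrolment has closed, the TB correction no longer changes entry, and the skin-cancer correction matters only while a subject is still taking study drug. The washout mismatch adds no weight, because its consequence is undetermined.

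The judgement about which version is intended rests on Sections 6.4.15 and 6.3.1.1 for TB, and on Section 7.1.4 and exclusion 607 for skin cancer.

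**What to change.** - **Exclusion 502.** Change the synopsis threshold to *one positive*. In both the synopsis and Section 4.2 502a, add *unless superseded by a negative repeat test under Section 6.4.15*. Keep the existing treatment exceptions.
- **Section 6.5.1.** Limit the exemption by adding *that has been fully resected* after the mention of non-melanoma skin cancer.
- **Exclusion 400 (optional).** State one washout rule in both places. Aligning the synopsis to 60 days is editorial; adopting the longer-of rule in Section 4.2 would be a substantive eligibility change, and the choice is the sponsor's.

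The first two changes cost a few words each and leave design, sample size and analysis as they are. If an amendment is no longer worthwhile, the sponsor should at least state which text governs when eligibility exceptions and protocol deviations are listed.

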APPENDIX 13. SPONSOR GUIDANCE ON STUDY CONDUCT DURING THE
CORONAVIRUS DISEASE 2019 (COVID-19) PANDEMIC.....132

LIST OF TABLES

Table 1: Schedule of Study Procedures16

Table 2: Induction and Active Treatment Dose Assignment.....40

Table 3: Thresholds for Vital Signs103

Table 4: ECG Interval Ranges103

LIST OF FIGURES

Figure 1: Study Design Schematic41

LIST OF ABBREVIATIONS AND DEFINITION OF TERMS

Abbreviation	Description
AE	adverse event
AESI	adverse events of special interest
ALT	alanine aminotransferase
ANCOVA	analysis of covariance
Anti-IL-12/23	interleukin 12/23 inhibitor
Anti-TNF	tumor necrosis factor inhibitor
AST	aspartate aminotransferase
ATE	active treatment extension
BCG	Bacille Calmette Guerin
BCRP	breast cancer resistance protein
b-HCG	beta human chorionic gonadotropin
BMI	body mass index
BP	blood pressure
CD	Crohn's disease
CDAI	Crohn's disease activity index
CDAI Clinical Remission	defined as CDAI < 150
CDAI Clinical Response	defined as CDAI reduction from baseline of ≥ 100 or CDAI < 150
CEC	Clinical Events Committee
CFR	(United States) Code of Federal Regulations
COVID-19	coronavirus disease 2019
CRF	case report form
[REDACTED]	[REDACTED]
CSR	clinical study report
CYP	cytochrome P450
DDI	drug-drug interaction
DNA	deoxyribonucleic acid
DVT	deep vein thrombosis
ECG	Electrocardiogram
eCOA	electronic clinical outcome assessments
EDC	electronic data capture
ELISA	enzyme-linked immunosorbent assay
Endoscopic Remission	defined as SES-CD2
Endoscopic Response	defined as SES-CD reduction of $\geq 50\%$ from baseline or endoscopic remission
EOS	End-of-Study
[REDACTED]	[REDACTED]
FDA	(United States) Food and Drug Administration
FSH	follicle stimulating hormone

Abbreviation	Description
GCP	Good Clinical Practice
GI	Gastrointestinal
H2 antagonists	Histamine H2 receptor antagonists
HBV	hepatitis B virus
HCV	hepatitis C virus
HIV	human immunodeficiency virus
HDPE	high-density polyethylene
HR	heart rate
IB	Investigator's Brochure
IBD	inflammatory bowel disease
IC ₅₀	quantity of a particular drug/substance needed to inhibit a given biological process by half
ICF	informed consent form
ICH	International Conference on Harmonization of Technical Requirements for Registration of Pharmaceuticals for Human Use
IDMC	Independent Data Monitoring Committee
IEC	Independent Ethics Committee
IgM	immunoglobulin M
INH	Isoniazid
INR	international normalized ratio
IP	investigational product
IRB	Institutional Review Board
IUD	intrauterine device
JAK	Janus kinase
MAD	multiple ascending dose
MedDRA	Medical Dictionary for Regulatory Activities (MedDRA [®])
mITT	modified intent to treat
mRNA	messenger ribonucleic acid
Modified SFAP Clinical remission	defined as abdominal pain score ≤ 1 , very soft/liquid stool frequency ≤ 1.5 , and both not worse than baseline
Modified SFAP-e Remission	defined as abdominal pain score ≤ 1 , stool frequency ≤ 1.5 , neither abdominal pain score or stool frequency worse than baseline, and SES-CD ≤ 2
NK	natural killer
[REDACTED]	[REDACTED]
PA	posterior anterior
Pack years	number of packs per day times number of years smoked
PD	Pharmacodynamics(s)
PI	principal investigator
P-gp	p-glycoprotein

Abbreviation	Description
PIC	powder in capsule
PK	pharmacokinetic(s)
PP	Per-protocol
PPI	proton-pump inhibitor
PRO	Patient-reported outcome
[REDACTED]	[REDACTED]
PT	preferred term
QD	Once daily
QTc	corrected QT interval
QTcF	Fridericia-corrected QT interval
REB	Research Ethics Board
RNA	ribonucleic acid
RT-PCR	reverse transcriptase polymerase chain reaction
RTSM	randomization and trial supply management
SAD	single ascending dose
SAE	serious adverse event
SAP	statistical analysis plan
SARS-CoV-2	severe acute respiratory syndrome coronavirus 2
SD	standard deviation
SES-CD	simplified endoscopy score for Crohn's disease
SFAP	Stool Frequency and Abdominal Pain
SFAP Clinical Remission	defined as abdominal pain score ≤ 1 , stool frequency ≤ 2.8 , and both not worse than baseline)
SFAP-e Remission	defined as abdominal pain score ≤ 1 , stool frequency ≤ 2.8 , neither abdominal pain score or stool frequency worse than baseline, and SES-CD ≤ 2
SOC	system organ class
SOP	standard operating procedure
STAT	signal transducer and activator of transcription
TB	Tuberculosis
TBPH	Theravance Biopharma, Inc.
TEAE	treatment-emergent adverse event
TNF	tumor necrosis factor
UC	ulcerative colitis
ULN	upper limit of normal
USP	United States Pharmacopeia

